4.5 Whole genome expression

As described above, whole genome mRNA expression profiles in colon tumor tissue will be interrogated to identify patterns of genes dysregulated in tumors. Various technologies have been developed to deduce and quantify the transcriptome, including hybridization-or sequence-based approaches. We propose to conduct RNA-Seq to profile the transcriptome to measure of levels of transcripts and their isoforms. Investigators at the Broad Institute and the Dana-Farber Cancer Institute have developed a methodology to routine conduct RNA-seq to profile the transcriptome from routine FFPE tumor specimens. These studies will allow a detailed examination of the impact of tumoral gene expression on patient outcome as well as an assessment of how tumoral gene expression may modify the influence of adjuvant celecoxib on patient survival.

The ability to discover and implement gene expression signatures on FFPE colon cancer blocks will allow us a unique opportunity to identify genes involved in celecoxib-mediated inhibition of colorectal carcinogenesis. In the future, genes identified in these analyses will be functionally characterized.

4.6 CpG Island Methylator Phenotype (CIMP)

A subset of colorectal adenocarcinomas displays an unusually high frequency and concordance of CpG island hypermethylation. This subset was first described by Toyota et al. as CIMP (CpG Island Methylator Phenotype) colorectal adenocarcinomas.¹³⁹ The definition of CIMP was recently refined, and was shown to underlie the majority of sporadic mismatch repair deficient colorectal adenocarcinomas and to be very tightly associated with BRAF mutation.¹³⁹ An improved panel of five markers (CACNA1G, IGF2, NEUROG1, RUNX3, and SOCS1) has been established to classify the CIMP phenotype, which outperforms other commonly used panels of CIMP in sensitivity and specificity.¹⁴²

CpG Island Methylator Phenotype (CIMP) will be analyzed using the MethyLight procedure at the USC Epigenome Center under supervision by [name] and [name] [name] as described.¹⁴²⁻¹⁴⁴ MethyLight technology utilizes real-time PCR analysis for bisulfite-based DNA methylation analysis. The USC Epigenome Center uses a non-methylation-dependent control reaction designed for a consensus Alu repetitive element sequence.¹⁴¹ This control reaction is a sensitive measure of very low DNA amounts, and is less prone to quantitation errors introduced by gene-copy anomalies, such as aneuploidy, gene amplification, deletions, etc., compared to a single-copy control reaction. MethyLight data are reported as a ratio between the value obtained for a methylation-specific reaction and that obtained for the methylation-independent Alu control reaction, normalized against similar measurements obtained for a fully methylated reference sample. The resulting output is expressed as "Percent of Methylated Reference (PMR)". The USC Epigenome Center has extensive experience with high-throughput DNA methylation analysis, and has established numerous quality control procedures. All reagents are prepared with dedicated or disposable vessels, solutions, and pipettes. Positive displacement pipettes or air-displacement pipettes with aerosol-resistant tips are used. Plate preparation is performed on a dedicated custom-built automated robotic platform based on the Qiagen BioRobot 3000. 10% of samples are repeated in duplicate randomly intermixed with the other samples as an additional quality control. Each bisulfite-converted DNA sample is

evaluated prior to MethyLight analysis using the Alu control reaction to ensure that sufficient bisulfite-DNA amounts are utilized in each CIMP-specific MethyLight assay.

LINE-1 methylation: To accurately quantify global DNA methylation, Pyrosequencing technology will be utilized in [name] laboratory.¹³⁴ PCR and subsequent Pyrosequencing for LINE-1 will be performed using the PyroMark kit (Biotage, Uppsala, Sweden). The PCR condition will be 45 cycles of 95C for 20 sec, 50C for 20 sec and 72C for 20 sec, followed by 72C for 5 min. The biotinylated PCR product will be purified and made single-stranded to act as a template in a pyrosequencing reaction, using the Pyrosequencing Vacuum Prep Tool (Biotage). Pyrosequencing reactions will be performed in the PSQ HS 96 System (Biotage). The nucleotide dispensation order will be: ACT CAG TGT GTC AGT CAG TTA GTC TG. Complete conversion of cytosine at a non-CpG site ensures successful bisulfite conversion. The amount of C relative to the sum of the amounts of C and T at each CpG site will be calculated as percentage. The average of the relative amounts of C in the 4 CpG sites will be used as overall LINE-1 methylation level in a given sample. Pyrosequencing to measure LINE-1 methylation has been previously validated.¹³⁴

Complementary to these techniques will be also the use of the Illumina EPIC DNA methylation array. This assay provides a genome-scale interrogation of the human methylome, with sampling of 862,927 CpG sites in the human genome, 2,932 non-CpG sites and 59 known SNPs. EPIC DNA methylation probes assays are located in nearly every gene in the genome (99% of Refseq genes have at least one CpG interrogated), with attention to gene promoters, enhancers, transcription factor binding sites, and miRNA promoter regions. EPIC probe content includes >90% of the HM450 content. Genomic DNA (250 ng) is bisulfite converted using the Zymo EZ DNA methylation kit. The amount of bisulfite-converted DNA as well as the completeness of bisulfite conversion for each sample are assessed using a panel of MethyLight-based real-time PCR quality control assays. Bisulfite-converted DNA is then repaired using the Illumina Restoration Kit. The repaired DNA is used as a substrate for the Illumina EPIC BeadArrays. After the chemistry steps, BeadArrays are scanned and the raw signal intensities are extracted from the *.IDAT files using the 'noob' function in the *minfi* R package. The 'noob' function corrects for background fluorescence intensities and red- green dye-bias. The beta value is calculated as $(M/(M+U))$, in which M and U refer to the (pre-processed) mean methylated and unmethylated probe signal intensities, respectively. Measurements in which the fluorescent intensity is not statistically significantly above background signal (detection p value > 0.05) are removed from the data set.

5.0 DATA ANALYSES

The primary efficacy variable for analyses will be disease-free survival (DFS). Secondary efficacy endpoints include recurrence-free survival (RFS) and overall survival.

It is hypothesized that specific tumor alterations will modify the effect of adjuvant celecoxib on patient survival. For the analysis of tumoral alterations (**Objective 1.1**), all patients who had a tumor block available will be included in the analysis. Within each of binary category of COX-2, VEGF, p21, beta-catenin, 15-PGDH, T cell overexpression, higher microvessel density, *PIK3CA* mutation, and microsatellite instability, the effect of celecoxib vs. placebo on DFS and OS will be examined. Cox proportional hazards models will be used to calculate HRs and 95% CIs for DFS and OS, adjusted for other prognostic factors. Tests for statistical interaction will be performed by entering into the model the cross-product term of the relevant biomarker with treatment assignment (celecoxib vs. placebo). Moreover, in Cox models, the main independent effect of each biomarker on DFS and OS will be assessed.

For plasma analytes (**Objective 1.2**: CRP, IL-6, and sTNF- α -R2), whether the effect of celecoxib vs. placebo on DFS differs according to baseline levels of each plasma inflammatory factor will be assessed. For primary analyses of survival, patients who died within three months of plasma collection will be excluded to minimize any bias due to occult cancer recurrence or preclinical illness. For these stratified analyses, each plasma analyte will be categorized into tertiles to maximize statistical power. Within each tertile of the specific plasma inflammatory factor, the effect of celecoxib vs. placebo on DFS and OS will be examined. Cox proportional hazards models will be used to calculate HRs and 95% CIs for DFS and OS, adjusted for other prognostic factors. Tests for statistical interaction will be performed by entering into the model the cross-product term of the plasma level as a continuous variable with treatment assignment (celecoxib vs. placebo).

In addition, the main effect of each plasma inflammatory factor on DFS and OS will be examined. For the main effect, plasma levels will be divided into quintiles for the analysis. Baseline characteristics of patients will be compared according to quintiles of the biomarker using Wilcoxon signed rank tests for continuous variables and chi-squared tests for categorical variables. For primary analyses of survival, patients who recurred or died within three months of plasma collection will be excluded to minimize any bias due to occult cancer recurrence or preclinical illness. In sensitivity analyses, the possibility of reverse causation will be assessed by allowing different lag times between plasma assessment and cancer recurrence or death. The log-rank test and Kaplan-Meier curves will be used to compare DFS OS by quintile of plasma level. Cox proportional hazards models will be used to control for multiple confounders. The two-tailed *P* value for the linear trend test across categories will be calculated using the plasma level as a continuous variable, consistent with prior studies.

The primary efficacy variable for analyses will be disease-free survival (DFS). Secondary efficacy endpoint will be overall survival.

For the main effect of plasma 25(OH)D (**Objective 1.3**), plasma 25(OH)D levels will be divided into quintiles for the analysis. Baseline characteristics of patients will be compared according to quintiles of the biomarker using Wilcoxon signed rank tests for continuous variables and chi-squared tests for categorical variables. For primary analyses of survival, patients who recurred or died within three months of plasma collection will be excluded to minimize any bias in the 25(OH)D level due to occult cancer recurrence or preclinical illness. In sensitivity analyses, the possibility of reverse causation will be assessed by allowing different lag times between 25(OH)D assessment and cancer recurrence or death. The log-rank test and Kaplan-Meier curves will be used to compare DFS OS by quintile of 25(OH)D level. Cox proportional hazards models will be used to control for multiple confounders. The two-tailed *P* value for the linear trend test across categories will be calculated using the 25(OH)D level as a continuous variable, consistent

with prior studies. In secondary analyses, we will examine how the relationship between 25(OH)D level and patient outcome is modified by relevant covariates such as ECOG performance status, treatment assignment, physical activity and body mass index, among others. Tests for statistical interaction will be performed by entering into the model the cross-product term of the plasma 25(OH)D as a continuous variable with the covariate as a continuous or binary variable.

For the analysis of tumoral alterations in vitamin D and related pathways (**Objective 1.4**), all patients who had a tumor block available for analysis of VDR expression, 1- α -hydroxylase, and KRAS mutation and data on circulating 25(OH)D concentration will be included. Tumoral protein overexpression will be defined as a) moderate/strong staining in any fraction of cells, or b) $\geq 50\%$ of tumor cells with weak staining. All tumors will be categorized as having VDR and 1- α -hydroxylase overexpression versus no overexpression, and KRAS mutated versus wild type. Within each of category of VDR expression, 1- α -hydroxylase expression, and KRAS mutational status, we will examine the influence of plasma levels of 25(OH)D divided into tertiles on DFS and OS. Tertiles will be utilized instead of quintiles of plasma 25(OH)D to maximize the ability to detect an association within each subgroup. Cox proportional hazards models will be used to calculate HRs and 95% CIs for DFS and OS, adjusted for other prognostic factors. Tests for statistical interaction will be performed by entering into the model the cross-product term of plasma 25(OH)D as a continuous variable with the molecular alteration as a binary variable (overexpressed versus not; mutated versus wild type).

In describing analyses related to gene expression, the genes/transcripts from RNA-seq will be referred to as features. The terms feature, feature expression and expression will also be used interchangeably. The maximum number of features is approximately 24,000. In these discussions, K will denote the number features (among the 24,000) which pass the non-phenotypic filters. The expressions, which are summary measures, are obtained following pre-processing. The background correction algorithm implemented by the BeadStudio software will be employed and quantile normalization will be applied to the background adjusted intensities.

Objective 1.5 is to identify the features from whole transcriptome analysis which are associated with DFS. As outliers in both the time-to-event observations and gene expressions may be encountered, the length of follow-up varies among patients, and multiple markers are considered, methods which are robust, are able to incorporate the censoring mechanism, and allow for incorporation of multiplicity adjustments will be employed. The association between the time-to-event endpoint and each of the features will be quantified using the non-parametric rank-covariance measure.¹⁴⁵ This method is a non-parametric counterpart to Cox regression where the time-to-event variable is regressed on the ranks of the expression. The family-wise error rate (FWER) adjusted exact permutation P-values will be calculated using B=10,000 permutation replicates. Features will be considered significant at the 0.05 FWER adjusted level.

We are interested in the association between each feature and DFS. Kendall's tau will be used to quantify these pairwise associations. This quantity is uniquely determined by the copula generating the joint (bivariate) distribution between each feature and DFS and as such is invariant to marginal distributions. It will be assumed that the marginal effects are continuous so as to ensure uniqueness of the generating copula.

An additional objective of gene expression assessment (**Objective 1.6**) is to identify those features for which there is expression by celecoxib interactions with respect to DFS. These analyses will be carried within the framework of two-way multiplicative Cox models.

The analyses outlined for the primary endpoint, will be carried out for OS and AE as well. For the adverse event endpoints, the two-sample Wilcoxon test will be employed to investigate the association between each feature and outcome.¹⁴⁶ For this endpoint, conditional inference tree and random forests methods for binary outcomes will be used.

The classification models for DFS, OS and adverse events in the previous models were based on molecular data. As additional exploratory analyses, the inclusion of clinical or demographic co-variables will be considered.

Functional annotation of discovered signature will be performed by Gene Set Enrichment Analysis (GSEA)¹⁶ using the Molecular Signature Database (MSigDB, [REDACTED]). Survival data analyses will be performed using the log-rank test and multivariate Cox regression. All analyses were performed using GenePattern¹⁸ [REDACTED] or the R statistical package [REDACTED].

For the analysis of CIMP (**Objective 1.7**), the primary efficacy variable for analyses will be disease-free survival (DFS). Secondary efficacy endpoints include recurrence-free survival (RFS) and overall survival (OS).

Baseline characteristics of patients will be compared according to CIMP-high vs. CIMP-low/0 using Wilcoxon signed rank tests for continuous variables and chi-squared tests for categorical variables. The log-rank test and Kaplan-Meier curves will be used to compare DFS and OS by CIMP-high vs. CIMP-low/0. Cox proportional hazards models will be used to control for multiple confounders including MSI, BRAF, and LINE-1 status. In secondary analyses, we will examine how the relationship between CIMP status and patient outcome is modified by relevant covariates such as age, ECOG performance status and treatment assignment, MSI, BRAF, and LINE-1 status among others. Tests for statistical interaction will be performed by entering into the model the cross-product term of the CIMP status (binary variable) with the covariate as a continuous or binary variable. The main independent effect of BRAF and LINE-1 status on DFS will also be assessed using the aforementioned COX models.

For the analysis of immune response (**Objective 1.8**), the primary efficacy variable for analyses will be disease-free survival (DFS). Secondary efficacy endpoints include recurrence-free survival (RFS) and overall survival (OS). Interactions with celecoxib randomized will also be determined.

The prognostic association of TIPC-based CRC subtypes and DFS will be determined, with stratification by celecoxib randomization. In exploratory analyses statistical interaction of TIPC subtype and F. nucleatum level will be assessed.

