5.4 Patient Registration/Randomization Procedures

The Oncology Patient Enrollment Network (OPEN) is a web-based registration system available on a 24/7 basis. OPEN is integrated with CTSU regulatory and roster data and with the Lead Protocol Organization (LPOs) registration/randomization systems or Theradex Interactive Web Response System (IWRS) for retrieval of patient registration/randomization assignment. OPEN will populate the patient enrollment data in NCI's clinical data management system, Medidata Rave.

Requirements for OPEN access:

- A valid CTEP-IAM account;
- To perform enrollments or request slot reservations: Be on a LPO roster, ETCTN Corresponding roster, or PO roster with the role of Registrar. Registrars must hold a minimum of an AP registration type;
- If a Delegation of Tasks Log (DTL) is required for the study, the registrar(s) must hold the OPEN Registrar task on the DTL for the site; and
- Have an approved site registration for a protocol prior to patient enrollment.

To assign an Investigator (IVR) or Non-Physician Investigator (NPiVR) as the treating, crediting, consenting, drug shipment (IVR only), or receiving investigator for a patient transfer in OPEN, the IVR or NPiVR must list the IRB number used on the site's IRB approval on their Form FDA 1572 in RCR. If a DTL is required for the study, the IVR or NPiVR must be assigned the appropriate OPEN-related tasks on the DTL.

Prior to accessing OPEN, site staff should verify the following:

- Patient has met all eligibility criteria within the protocol stated timeframes; and
- All patients have signed an appropriate consent form and HIPAA authorization form (if applicable)

Note: The OPEN system will provide the site with a printable confirmation of registration and treatment information. Please print this confirmation for your records.

To receive site reimbursement for specific tests and/or bio-specimen submissions, completion dates must be entered in the OPEN Funding screen post registration. Please refer to the protocol-specific funding page on the CTSU members' website for additional information. Timely entry of completion dates is recommended as this will trigger site reimbursement.

Access OPEN at [REDACTED] or from the OPEN link on the CTSU members' website. Further instructional information is in the OPEN section of the CTSU website at [REDACTED]. For any additional questions, contact the CTSU Help Desk at [REDACTED].

Treatment is to begin within 14 days of randomization.

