5.5 Registration to companion studies

There are three substudies within CALGB/SWOG C80702. These correlative science studies **must be offered to all patients** enrolled on CALGB/SWOG C80702 (although patients may opt to not participate). These substudies do not require separate IRB approval. The substudies included within CALGB/SWOG C80702 are:

- CALGB 150911: Correlative science companion studies for CALGB/SWOG C80702 ([Appendix II](#))
- CALGB 60905: Pharmacogenetic companion studies for CALGB/SWOG C80702 ([Appendix III](#))
- CALGB 71002: Cancer prevention companion studies for CALGB/SWOG C80702 (Appendices [IV](#) and [V](#))

If a patient answers “yes” to “I agree that my specimen may be used for the research studies described above”, question #2 in the model consent, they have consented to participate in the studies described in [Appendix II](#). The patient should be registered to CALGB 150911 at the same time they are registered to the treatment trial (CALGB/SWOG C80702). Samples should be submitted per [Sections 5.8.1](#), [5.8.2](#), [5.8.3](#), and [5.8.4](#).

If a patient answers “yes” to “I agree that my blood may be used for the genetic research studies described above”, question #3 in the model consent, they have consented to participate in the studies described in [Appendix III](#). The patient should be registered to CALGB 60905. Samples should be submitted per [Section 5.8.5](#).

If a patient answers “yes” to “I choose to take part in the cancer prevention studies and agree to complete the diet and lifestyle questionnaire”, question #1 in the model consent, they have consented to participate in the cancer prevention studies described in Appendices [IV](#) and [V](#). Questionnaires and reports should be submitted per [Section 5.9](#).

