6.0 REQUIRED DATA

Pre-Study Testing Intervals

To be completed within 16 DAYS before registration:

- All bloodwork, history and physical, and pregnancy test.

To be completed within 80 DAYS before registration (preoperative scans acceptable):

- CT or MRI abdomen/pelvis or PET-CT scan without evidence of metastatic disease
- CT chest or chest X-ray (PET-CT including chest, is acceptable) without evidence of metastatic disease

	Prior to Registration*	Day 1 of each tx w/ FOLFOX*	During tx w/ Celecoxib Placebo only**	Post-tx Follow Up***
Tests & Observations				
History and Physical Examination	X	A	X	X
Pulse, Blood Pressure	X	A	X	X
Height	X			
Weight/Body Surface Area ϕ	X	X	X	X
Performance Status	X	A	X	X
Drug Toxicity Assessment		X	X	X
Celecoxib/Placebo Adherence#		B	B	
Laboratory Studies				
CBC, Differential, Platelets	X	X		
Serum Creatinine and BUN	X	C	F	
AST, Alk Phos., Total Bilirubin	X	C	F	
PT/INR	D	D	D	
Pregnancy Test (UCG) ‡	X			
CEA	X		E	E
STAGING				
Chest x-ray (PA & Lateral) or Chest CT	X		E	E
Abdominal/pelvic Imaging: (CT, MRI or PET-CT scan)	X		E	E
Companion Studies Ψ				
Diet & Lifestyle / Other Meds / Comorbidities Questionnaire	To be completed w/in first 6 weeks of randomization and 14-16 months after randomization. See Section 5.9.			
Colonoscopy and Pathology Reports	See Section 5.9.			
Tumor Block	To be collected pre-treatment (see Section 5.8).			
Whole Blood, Plasma, and Serum	To be collected pre-treatment (see Section 5.8).			

* Pre-registration H&P, vital signs, labs and clinical assessments may be used for Day 1 of Cycle 1. For subsequent cycles, H&P and labs may be obtained within 72 hours prior to day of treatment (96 hours if due to holidays).

** Every 3 months until 3 years after initiation of celecoxib/placebo or until disease progression, whichever comes first.

*** Every 6 months until 6 years after randomization or until disease progression, whichever comes first. Once a patient has progressive disease, submission of follow-up forms is still required for survival data. See forms schedule in [Section 5.7](#).

A While on FOLFOX, patients should have a physical exam and report capsule counts of celecoxib/placebo prior to cycles 3 and 5 for study arms C and D and prior to cycles 3, 5, 7, 9 and 11 for study arms A and B. If treatment is held due to toxicity, physical exam and capsule count does not need to be repeated on the day that therapy is resumed.

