7.0 TREATMENT PLAN

Initiation of treatment must begin within 14 days after randomization. While not strictly an eligibility criterion, it is strongly recommended that patients begin treatment between 21 - 56 days after surgery. For patients who fall outside of this range or for any treatment-related questions, contact the Alliance or SWOG Study Chair.

This is a randomized, double-blind trial. No blinded starter supplies will be available for this study. Initial blinded, patient-specific clinical supplies of celecoxib / placebo will be shipped from the Pharmaceutical Management Branch (PMB) to the registering investigator at the time of patient randomization and should arrive within 7 to 10 days of randomization (see [Section 9.4](#)).

One cycle will be defined as 14 days of treatment. Cytotoxic chemotherapy will consist of 6 or 12 cycles of FOLFOX and daily celecoxib/placebo. Celecoxib/placebo will start by Day 1 of cycle 2 of FOLFOX.

7.1 FOLFOX, every 2 weeks.

- **Oxaliplatin** 85 mg/m² IV over two hours, **followed by**
- **Leucovorin** 400 mg/m² IV over two hours. Alternatively, leucovorin may be administered (via separate infusion containers) concurrently with oxaliplatin, **followed by**
- **5-FU** 400 mg/m² IV bolus, then 2400 mg/m² continuous IV infusion over 46-48 hours.

Patients receiving oxaliplatin on this study should be counseled to avoid cold drinks, chewing of ice chips, and exposure to cold water or air because the neurotoxicity often seen with oxaliplatin appears to be exacerbated by exposure to cold. The period of time during which the patient is at risk for these cold-induced sensory neuropathies is not well documented. Patients should exercise caution regarding cold exposure during the treatment period. Peripheral sensory neuropathies can occur at any time after receiving oxaliplatin therapy.

Continuous infusion 5-FU should be administered as specified, though early pump shut-offs do not need to be reported on forms unless >10% of dose was not administered.

In the event of a leucovorin shortage, refer to the CALGB 80702 study page, which can be found on the Alliance and CTSU websites.

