13.0 STATISTICAL CONSIDERATIONS

13.1 Sample Size and Power Estimates

The primary endpoint of this trial is DFS measured from study entry (time of randomization) until documented progression or death from any cause. The superiority hypothesis of celecoxib use will be tested in this patient population using the DFS endpoint. Non-exponential survival is expected. Based on the findings from NSABP C07 and the MOSAIC trials, the DFS distribution under the null hypothesis assumes probabilities of failure by year for years 1 through 6 to be 0.10, 0.12, 0.06, 0.05, 0.03 and 0.02, respectively. It is anticipated that 2,500 patients will be enrolled in 3.125 years (800 patients per year) with a follow-up period of 3 years.

The number of expected DFS events at the conclusion of the trial ($n=775$) is estimated using the method proposed by Schoenfeld. A hazard ratio of 0.79 in favor of celecoxib is assumed; this corresponds to an increase in the probability of being disease-free at 3 years from 0.72 to 0.77. With 775 events observed, this difference can be detected with power of approximately 0.91 (2-sided $\alpha=0.05$). The stratified log rank test will be used to test the primary hypothesis, with stratification on the number of lymph nodes (1-3; ≥ 4) and aspirin use (no; yes).

Overall survival (OS) measured from study entry (time of randomization) until death from any cause will be studied as a secondary endpoint.

In addition, a prospective international effort is underway to pool patient level data from multiple trials that will test the duration assumption (the IDEA trial; see [Appendix VI](#)). Our goal is for the United States Intergroup to contribute 2500 patients with stage III colon cancer to this effort. Data provided to the IDEA trial will be fully de-identified. Alliance Statistics and Data Center at Duke University will maintain the data link between the coded patient numbers provided in the de-identified dataset and the patient study ID numbers. Any interim transfer of data must be approved by the Alliance Data and Safety Monitoring Board.

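### The primary celecoxib-by-plasma-marker analysis (Appendix II, Objective 1.2) drops patients who died within three months, a post-randomisation exclusion on part of the outcome that its stated reason does not justify; the likely effect is small

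*Combined protocol and SAP*

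**What the plan says.** Appendix II section 5.0 asks, for Objective 1.2, whether the celecoxib effect on DFS depends on baseline CRP, IL-6 and sTNF-α-R2. The primary survival analyses carry the rule that "patients who died within three months of plasma collection will be excluded to minimize any bias due to occult cancer recurrence or preclinical illness". The text then moves straight to the stratified comparison: "Within each tertile of the specific plasma inflammatory factor, the effect of celecoxib vs. placebo on DFS and OS will be examined". A cross-product term of continuous marker level and treatment arm tests the interaction. The exclusion thus governs a randomised contrast and is labelled primary.

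Related provisions:

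- **Endpoint.** Section 13.1 defines "DFS measured from study entry (time of randomization) until documented progression or death from any cause", and OS as time from randomisation to death from any cause. Appendix II section 6.0 adopts the treatment protocol's definitions.
- **Sample timing.** Section 6.0 of the protocol lists plasma as "To be collected pre-treatment", and section 5.5 says "The patient should be registered to CALGB 150911 at the same time they are registered to the treatment trial".
- **Exposure.** Section 5.4: "Treatment is to begin within 14 days of randomization". Section 7.0: "Celecoxib/placebo will start by Day 1 of cycle 2 of FOLFOX"; a cycle is 14 days.
- **Parallel analysis.** For Objective 1.1 (celecoxib by tumour marker, same section), "all patients who had a tumor block available will be included in the analysis".
- **Marker main effects.** The next paragraphs of section 5.0 exclude patients with either recurrence or death within three months, and add sensitivity analyses with different lag times. Neither lag-time analyses nor an all-patient analysis is stated for the celecoxib contrast.

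**The concern.** Occult recurrence or preclinical illness at the blood draw can distort an association between a marker and outcome, because the illness may raise the marker and also cause the early event. That is a reason for a lag in a prognostic analysis. It does not confound celecoxib versus placebo, because randomisation balances such illness between arms in expectation.

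Removing patients because they died early conditions on something that happens after randomisation and that treatment could affect. If early deaths differed by arm, the difference would vanish from this analysis. If they also clustered at high marker levels, where Appendix II section 3.0 expects the greater benefit, part of a true interaction would vanish too.

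**Working it through.** **1. What is being excluded.** Plasma is drawn before treatment, at about the time of registration, so the three-month window starts close to randomisation. Study drug is due at most about 14 + 14 = 28 days after randomisation if nothing is delayed, so roughly two of the three months are on study drug. Among randomised patients, every excluded death is an OS event and belongs to a patient with a DFS event.

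**2. What the rule does to each endpoint.**

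- OS: no events remain before three months and later risk sets are unchanged. This is in effect a three-month landmark analysis, estimating an effect conditional on surviving three months.
- DFS: a patient who recurs at month 2 and is alive at month 3 stays in; one who recurs at month 2 and dies before month 3 is removed. Inclusion can depend on what happens after the DFS event, and the early recurrences that the rationale is about are kept.

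**3. Reproducing the plan's power.** Appendix II Table 3 gives 0.34, 0.58 and 0.71 for an interaction hazard ratio of 1.5 with 1,500 patients and 465 events. With four equal cells, power = Φ(ln(HR)·√events/4 − z). Here ln(1.5)·√465/4 = 2.186, giving 0.348, 0.589 and 0.706 at two-sided α = 0.01, 0.05 and 0.10. All 18 Table 3 powers reproduce within 0.02, so the planning figures are sound.

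**4. Events and power lost.** Three-month mortality is not in the documents. I assume 0.25% to 2.5%. The only early figure given, 1.8% at 60 days with FOLFOX (section 1.4), is for advanced disease and serves as a high reference.

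- 0.25%: 1,500 × 0.0025 = 3.75 deaths, 0.8% of 465; power at α = 0.05 becomes 0.586.
- 2.5%: 37.5 deaths, 8.1% of 465; power becomes 0.554.

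The loss is at most 3.5 percentage points.

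**5. Bias on the documents' cardiovascular rates.** Section 1.8, Table 2, gives composite rates per 1,000 patient-years. With 750 per arm for 0.25 years (187.5 patient-years), about 232.5 DFS events per arm, and every event taken as fatal:

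| Rates, placebo vs celecoxib | Events in 3 months | Excess | HR multiplier after exclusion |
|---|---|---|---|
| 400 mg once daily, 8.6 vs 9.6 | 1.61 vs 1.80 | 0.19 | (232.5 − 1.80)/(232.5 − 1.61) = 0.9992 |
| All doses, 7.5 vs 11.2 | 1.41 vs 2.10 | 0.69 | 0.9970 |
| 400 mg twice daily, 4.6 vs 13.9 | 0.86 vs 2.61 | 1.74 | 0.9925 |

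The shift is 0.1% to 0.8%. It is overstated, because the composite includes non-fatal events.

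**6. Bias under assumed early mortality.** Cox simulation with 1,500 patients, section 13.1's yearly failure probabilities and 2,000 runs per row; overall celecoxib hazard ratio:

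| 3-month deaths, placebo vs celecoxib (assumed) | Later HR | All patients | Early deaths excluded |
|---|---|---|---|
| 0.5% vs 0.5% | 1 | 0.998 | 0.998 |
| 2% vs 2% | 1 | 1.000 | 1.000 |
| 0.5% vs 0.5% | 0.79 | 0.791 | 0.788 |
| 0.5% vs 1% | 0.79 | 0.808 | 0.791 |
| 1% vs 2% | 0.79 | 0.824 | 0.791 |

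The last two rows shift by 0.791/0.808 = 0.979 and 0.791/0.824 = 0.960, about 2% and 4%. In the two null rows, rejection rates at nominal 0.05 lie between 0.040 and 0.061 for the treatment and interaction tests (Monte Carlo standard error about 0.005), and the exclusion changes none by more than 0.004.

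With excess early deaths only in the upper marker half (0.5% in both arms of the lower half; 3,000 runs), 1% vs 2% gives an interaction hazard ratio of 1.030 with all patients and 1.001 after exclusion; 1% vs 3% gives 1.059 and 1.001.

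**The case against.** The best defence is that the rule is a landmark in all but name. For OS that is right: with equal early mortality the hazard ratio and type I error are essentially unchanged. It is not right for DFS, where early recurrences stay in.

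A second defence is that reverse causation has some bearing on an interaction. If occult illness raises CRP or IL-6, tertile membership partly reflects that illness rather than background inflammation. This stands as a reason for a sensitivity analysis. It does not justify a primary exclusion, and a death-only rule addresses it poorly because it retains early recurrences.

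A reader might infer that the rule breaks the treatment comparison, or that it hides celecoxib's cardiovascular deaths from the trial. The documents support neither. Bias needs early mortality that differs by arm, and nothing in the documents shows that. The primary DFS analysis counts all deaths from randomisation, cardiovascular events have their own objective (2.2.5) and expedited reporting of grades 2 to 5 (section 14.2), and section 4.3.7 excludes several high-risk cardiac histories. Only a consent-dependent companion analysis is touched.

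**Conclusion.** The point holds as a small defect in a companion analysis. The primary Objective 1.2 contrast uses an outcome-based, post-randomisation exclusion whose stated reason mainly concerns marker-outcome associations. It is inconsistent with Objective 1.1 and with the main-effect rule a few lines later, and no all-patient analysis is stated as a check.

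There is no material bias if early mortality is equal by arm, and under 1% on the hazard ratio using the protocol's cardiovascular rates. The 2% to 4% figures rest on assumed mortality differences with no source in the documents. The direction follows whichever arm has the excess early deaths: exclusion flatters celecoxib only if the excess is on celecoxib. The trial's primary DFS result is not affected.

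**What to change.** In Appendix II section 5.0, Objective 1.2:

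- Make the primary celecoxib-by-analyte analysis, both within tertiles and for the interaction test, include all randomised patients with a plasma sample. State that the protocol's DFS and OS definitions from randomisation apply, as Appendix II section 6.0 already implies.
- Confine the three-month exclusion to the marker main-effect analyses, or present it for the celecoxib contrast as a labelled sensitivity analysis.
- Reconcile the death-only rule for the celecoxib contrast with the recurrence-or-death rule for main effects, and give the reason for whichever is kept.

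This is a change of a few sentences. It needs no new data, samples or patients, keeps every event assumed in Table 3, and aligns Objective 1.2 with Objective 1.1.
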